The following data is in preparation for publication. Data was collected retrospectively for all patients transplanted between 3/14/2006 to 12/31/2007 at The University of Toledo Medical Center. There were *no exclusion criteria* other than limiting data to two transplant surgeons resulting in a study population of 143 patients. The first study group was given Prograf® (P) alone (47 patients) following transplantation, with the later group receiving Prograf® and myfortic® (P/M) (96 patients). Prograf® target level was 8 -12 ng/ml for both groups and myfortic® target dose was 720 mg PO bid adjusted for diarrhea and leukopenia. All patients were treated with Valcyte® and Bactrim® prophylaxis for 6-12 months. Review of the study populations showed no significance differences between the two immunosuppression groups for demographic details, death censored graft survival, patient survival, graft survival, rejection rate, one or two year creatinine level, severity of rejection (Banff score) or humoral rejection. Death censored graft survival rates after one year were 97.8% (P) and 89.4% (P/M). Two year death censored graft survival was 88.9% (P) and 85.6% (P/M). One year patient survival was 93.6% (P) vs 95.8% (P/M) and two year patient survival was 93.6% (P) vs 90.6% (P/M). Creatinine level at one year was 1.7±1.2 mg/dL (P) and 1.5±0.6 mg/dL (P/M) and at two years was 1.7±1.3 mg/dL (P) and 1.5±0.4 mg/dL (P/M). One year overall biopsy-proven rejection rates were 21.3% (P) vs 15.6% (P/M) and two year overall biopsy-proven rejection rates were 25.5% (P) vs 19.8% (P/M). Though not achieving statistical significance, our analysis demonstrated a trend toward differences in response to therapy based on ethnicity. At two years, rejection rates were 22.6% for Caucasians in both study groups, whereas in African-Americans, rejection rates were 45.5% (P) and 13% (P/M) (p=0.0789). While observing a 45% rejection rate in African-Americans treated with Prograf® in the absence of myfortic®, this increased rejection rate did not correspond to worsening two year graft survival that was 90.9%. Like the Miami experience, our data suggests caution with Campath® induction in African Americans, with two caveats: 1) our increased rejection rates were only seen in the absence of myfortic®; and 2) in the Miami study their results were limited by lower Prograf® bioavailability in African Americans.

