After publication of the study by Hanaway et al. in NEJM in late 2011, we decided that our 15-20% rejection rate with Prograf® and myfortic® with no steroid taper was unacceptable.¹⁸ Therefore, we modified our protocol to eliminate the second dose of 500 mg methylprednisolone intraoperatively and instead have spread this out by adding a steroid taper for the first five days post-operatively as was done in the Hanaway study. Since adopting this policy, we have seen a significant reduction in our rejection rate.

Everolimus (Zortress®) inhibits the proliferation (growth or production) of T and B cells. It is an inhibitor of intracellular signal transduction (the relaying of signals inside a cell that communicates to the cell that it should activate or change) that targets the

mammalian target of rapamycin (mTOR). The mechanism of action of everolimus appears to be distinct from those of calcineurin inhibitors. It forms a complex with the cytoplasmic protein FKBP-12 (intracellular tacrolimus-binding protein) and binds to and interferes with the function of FRAP. FRAP is a key regulatory protein which governs cell metabolism, growth and proliferation. The blockage of this signal leads to inhibition of cell cycle progression from G1 to the S phase (cell cycle growth phases); thus not allowing cells to develop and multiply. Combining everolimus and a calcineurin inhibitor gives rise to synergistic immunosuppressive properties.

Tacrolimus (Prograf® or Hecoria®) inhibits T-lymphocyte activation, although the exact mechanism of action is not known. Experimental evidence suggests that tacrolimus binds to an intracellular protein, FKBP-12. A complex of tacrolimus-FKBP-12, calcium, calmodulin, and calcineurin is then formed and the phosphatase activity (enzyme that frees or removes phosphate from a chemical reaction) of calcineurin is inhibited. This effect may prevent the dephosphorylation (removal of a phosphate group) and translocation (chromosome rearrangement) of nuclear factor of activated T-cells (NF-AT), a nuclear component thought to initiate gene transcription for the formation of lymphokines (substances released by activated T-cells such as interleukin-2 or gamma interferon). The net result is the inhibition of T-lymphocyte activation (i.e., immunosuppression).

Study Purpose and Rationale

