It is now clear that immunosuppressive strategies for renal transplantation achieve excellent short-term and medium-term results. Unfortunately, the long-term results have not substantially improved in the last 20 years. The reasons for this failure to achieve better long-term results are complicated and include such things as allowing older and sicker people to be recipients, using poorer quality donor kidneys and the complications associated with long-term immunosuppression. Among the worst of the long-term effects of chronic immunosuppression are the nephrotoxicity of the calcineurin inhibitors and the myriad complications of steroids. The goal of many now in the transplant field is to limit the exposure of transplant recipients to both steroids and calcineurin inhibitors. The following protocol evaluates the reduction of calcineurin inhibitors in a protocol that has already successfully eliminated the long-term use of steroids. Given the substantial experience with Campath® detailed above, the following study protocol will be offered to all patients undergoing renal transplantation at the University of Toledo University Medical Center. This is a small pilot study; multiple comparisons will be made for descriptive purposes only.

Hypothesis:

Our hypothesis is that conversion to everolimus (Zortress®), allowing the reduction of calcineurin inhibitors, will reduce nephrotoxicity (measured by increased creatinine clearance) and lengthen overall graft survival (measured by 2-year graft survival).

Objectives:

1. The primary objective of the study is to compare the efficacy and the effects on renal function of calcineurin-inhibitor reduction with conversion at 2 months after transplantation to Reduced Dose tacrolimus/everolimus in adult renal transplant recipients. Efficacy will be defined using two co-primary endpoints.
 - a. A composite efficacy end point [treated biopsy-proven rejection (BPAR), graft loss, death or loss to follow-up].
 - b. Renal function at 24 months post transplantation using GFR as measured by the Modified Diet Renal Disease (MDRD) estimation.

2. Secondary objectives will be to:
 - a. Compare the safety and tolerability of the experimental arm compared to the historical control arm.
 - b. Compare the presence of proteinuria as defined by spot urine protein to creatinine ratio greater than 1.0 in the experimental arm to the historical control arm.

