 - Adequate barrier methods of contraception include: diaphragm, condom (by the partner), intrauterine device (copper or hormonal), sponge or spermicide. Hormonal contraceptives include any marketed contraceptive agent that includes an estrogen and/or a progestational agent. Acceptable contraception methods will be discussed with all women of child-bearing potential.

- Reliable contraception should be maintained throughout the study and for 8 weeks after study drug discontinuation. For women who become pregnant while using Myfortic® or within 8 weeks of discontinuing therapy, we will report the pregnancy to the Mycophenolate Pregnancy Reference Registry ([name]) and will strongly encourage the patient to enroll in the pregnancy registry.
- Women are considered post-menopausal and not of child bearing potential if they have had 12 months of natural (spontaneous) amenorrhea with an appropriate clinical profile (e.g. age appropriate, history of vasomotor symptoms) or six months of spontaneous amenorrhea with serum FSH levels > 40 mIU/mL and estradiol < 20 pg/mL] or have had surgical bilateral oophorectomy (with or without hysterectomy) at least six weeks ago. In the case of oophorectomy alone, only when the reproductive status of the woman has been confirmed by follow up hormone level assessment is she considered not of child bearing potential.

Study Duration:

We plan to enroll 11 patients per year. Given this assumption, the enrollment will take five years. Adding two years of follow-up care, we will be able to complete the study in 7 years.

Study Design:

1. Single center pilot study utilizing historical control
2. A single treatment arm
3. Eleven patients per year
4. Five years to enroll 55 patients.
5. Enroll all patients who meet the inclusion criteria at 2 months and up to 6 months (± 10 days) post kidney transplantation and are willing to consent for this trial.
6. Patients would have study visits, serum creatinine measurements and other clinically relevant parameters measured monthly until 6 months, then q3 months until 2 years post-transplantation.
7. Graft survival would be measured by the absence of the need for dialysis.
8. It would not be mandatory, but a renal biopsy would be recommended at 2 years to look for underlying early signs of calcineurin toxicity/chronic allograft nephropathy.

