9. Secondary endpoints would include such parameters as post-transplant diabetes, proteinuria, lipid levels, mouth sores, neurotoxicity, pneumonitis, CMV, PTLN, BK-nephropathy, malignancies, cardiovascular complications, etc.
10. Our historical control will be composed of patients transplanted at the University of Toledo Medical Center between October 2011 and the beginning of this trial. All of those patients will have been treated with the exact same protocol as in this study except that they will not have been converted to the treatment arm above, but will have remained on tacrolimus and myfortic®, unless the clinical situation warranted changing immunosuppression. We expect that the control group will consist of approximately 50-55 patients and will have similar demographics to the patients that will be enrolled in this trial, given that we will use the same inclusion and exclusion criteria to select all patients from October 2011 until the start of this trial to populate

the historical control group. The reason for October 2011 as the starting point for the historical control is that this is the date when we modified our protocol to add a five day taper of steroids immediately after transplantation. Prior to that we only gave steroids immediately prior to the transplantation procedure. Thus, to be consistent with the patients in this trial, we believe the most accurate historical control should have the same treatment with steroids perioperatively. We will utilize all patients available in the historical control dataset and will not attempt to match for the demographics present in the experimental arm. The control group will consist of a historical control; prospective patients who are not willing to participate in the study will not be considered part of the control group.

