This will be a small, pilot study to test whether conversion to everolimus (Zortress®), allowing the reduction of calcineurin inhibitors, will reduce nephrotoxicity (measured by increased creatinine clearance) and lengthen overall graft survival (measured by 2-3 year graft survival). As it is not a large study (55 patients, 11 patients per year), it is not powered to achieve statistical significance. The statistical significance will also be impaired by the use of a historical control group. However, the data generated will be published irrespective of the results, thus making the data available for meta-analysis.

This trial is designed as a parallel-group study. Analysis of data for this design is simple and interpretation of the result is straightforward. Given the limited number of

patients in the trial it may not be meaningful to apply analysis of (co)variance for the statistical evaluation of a continuous variables such as creatinine clearance, but we will attempt to use this method with the guidance of our statistician, [name].^{19,20} Likewise, the limited number of patients in the trial may prevent meaningful analysis of time-to-event variables such as graft survival. Nonetheless, we will work with [name] to use methods appropriate for survival analysis including the Kaplan-Meier method and Cox's proportional hazards regression to see if meaningful differences exist between our study groups and our historical control.^{21,22} If warranted, for safety analyses the AEs and SAEs could be summarized by treatment group but no statistical tests performed due to the population size as a pilot study. In addition, the PI and Co-PI will meet with other members of the clinical transplant team to review the results of this study on a quarterly basis to ensure that no significant adverse events warrant the discontinuation of the trial. Given the small number of patients in the trial, we will analyze the data after we have enrolled 10 patients. If the study immunosuppression regimen has a > 40% Banff 2a rejection rate or greater than 20% patient death rate, then that arm will be prematurely terminated. Serious adverse events will also be analyzed and may serve as grounds for study discontinuation.

Everolimus IIRP Pilot Study Evaluation and Visit Schedule

Treatment Period															
			Months												
	Screening (Visit 1)	Baseline (Visit 2)	1 (3)	2 (4)	3 (5)	4 (6)	5 (7)	6 (8)	9 (9)	12 (10)	15 (11)	18 (12)	21 (13)	24 (14)	

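### The caution about the historical control is ambiguous and incomplete: the planned analyses omit between-period variation, so nominal intervals understate uncertainty, and drift may bias the estimate either way

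*Combined protocol and SAP*

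**What the plan says.** The Statistical Section states that the study is small and that "it is not powered to achieve statistical significance". The next sentence adds "The statistical significance will also be impaired by the use of a historical control group". It then commits to publishing whatever the result, "thus making the data available for meta-analysis". The following paragraph labels the design parallel-group and calls its interpretation straightforward. It names analysis of (co)variance for continuous outcomes, and Kaplan-Meier and Cox regression for time-to-event outcomes, against the historical control.

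Study Design gives the two groups. For the trial arm, item 4 says "Five years to enroll 55 patients". For the controls, item 10 says "We expect that the control group will consist of approximately 50-55 patients", transplanted from October 2011 up to the start of the trial. The same eligibility criteria apply to both groups, and there is no demographic matching. Study Purpose and Rationale adds that "multiple comparisons will be made for descriptive purposes only".

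Drift, period effects, between-period variance and false-positive risk are not mentioned anywhere.

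**The concern.** The caution follows directly on the statement about power and is joined to it by the word *also*. It can therefore be read as naming a second obstacle to reaching significance. The planned models do not behave that way. All controls come from before the trial and all everolimus patients are enrolled after it starts, so period and treatment cannot be separated. The models' standard errors hold only within-group sampling error. Any difference between the periods goes into the estimated treatment difference, with no allowance for it in the P value or interval.

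What is at stake is the published estimate and its standard error. A reader has no warning that the interval is too narrow, and a meta-analyst using inverse-variance weights would give the comparison too much weight. The parallel-group label makes both more likely.

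**Working it through.** **The plan's own figure.** 11 patients per year × 5 years = 55, which reproduces. This is accrual arithmetic. No power, alpha or effect size is stated, so a two-sided 5% level is assumed below.

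**Does the historical control weaken nominal significance?** In outcome-SD units, SE = √(1/n₁ + 1/n₂).
- 55 v 55: 0.191. 55 v 50: 0.195. These equal the SEs for concurrent groups of the same size.
- The same 55 patients randomised 28:27: 0.270.

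On the nominal calculation it does not.

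**What is left out.** Let the period shift be random with mean 0 and SD τ. Then:
- true SE = √(SE² + τ²)
- type I error of a nominal 5% test = 2Φ(−1.96 × SE / true SE)
- coverage of a nominal 95% interval = 1 minus that
- excess inverse-variance weight = (SE² + τ²) / SE²

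τ is not in the documents, so every value of it is an assumption.

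**Generic scale, 55 v 55**

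| τ (outcome SDs) | Type I error | Coverage | True / nominal width |
|---|---|---|---|
| 0 | 5.0% | 95.0% | 1.00 |
| 0.1 | 8.3% | 91.7% | 1.13 |
| 0.2 | 17.6% | 82.4% | 1.45 |
| 0.3 | 29.3% | 70.7% | 1.86 |

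Simulation of 20,000 t-tests per row gave type I errors of 5.1%, 8.3%, 18.0% and 29.1%.

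**Composite endpoint.** Assumed rate p = 15% or 20% in both groups, with 55 v 50-55 patients. SE = √(p(1−p)(1/55 + 1/n₂)), which runs from √(0.1275 × 2/55) = 0.068 to √(0.16 × (1/55 + 1/50)) = 0.078.

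| τ (points) | Type I error | Coverage | 95% half-width (points) | Excess weight |
|---|---|---|---|---|
| 0 | 5% | 95% | 13.3-15.3 | 1.00 |
| 3 | 6.7-7.3% | about 93% | 14.6-16.4 | 1.15-1.19 |
| 5.7 | 11-13% | 87-89% | 17.4-19.0 | 1.53-1.70 |

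**Fixed shift, no treatment effect.** Exact enumeration of two binomials with an uncorrected chi-square test, used here as a simple stand-in for the planned models. If the period alone lowers the trial arm's risk by 3, 5.7 or 10 points, the false-positive rate is 6.7-7.3%, 12-14.6% or 30-42.5%.

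**Fixed shift against a real benefit.** True risks of 5% v 20%, 55 v 55: power is 69%. If drift lowers the control risk by 5.7 points to 14.3%, power falls to 38%. Here the P value tends to be too large.

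**GFR.** Assumed SD 15-20 and τ = 3 mL/min/1.73 m², neither from the documents. SE runs from 15√(2/55) = 2.86 to 20√(1/55 + 1/50) = 3.91, giving a type I error of about 18% down to 12%.

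**The case against.** **The word *impaired* may mean less trustworthy.** This stands as a possible reading. On it, the sentence is incomplete rather than wrong. A reader might infer that the plan claims a conservative comparison, but no part of it says so, and the surrounding text discourages reliance on significance.

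**Significance really would be harder to reach if period variance were counted.** This is true: for a 0.5 SD effect, power falls from 75% to 44% at τ = 0.2 SD. But the plan describes no such analysis, and the methods it names do not do this by default.

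**P values are not always too small.** This also stands. They are too small on average under no effect with random drift. A fixed drift opposing a real benefit does the reverse, as the 69% to 38% example shows. A replacement caveat must not claim one direction.

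**The illustrative sizes have weak anchors.** They do. The 5.7 points is the gap in one-year rejection between the centre's two 2006-07 cohorts (21.3% of 47 v 15.6% of 96). Its sampling SE is √(0.213 × 0.787/47 + 0.156 × 0.844/96) = 7.0 points, larger than the gap, and the regimen differed too. It is not a measured drift. The 15-20% rate is also assumed. The centre's nearest figures predate October 2011, since when the background section reports "Since adopting this policy, we have seen a significant reduction in our rejection rate", and eligibility requires no rejection before screening. That October 2011 change applies to both groups, so it is not a known bias here.

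**The trial is descriptive, with no stated alpha.** No formal decision is at risk. Estimates, intervals and standard errors are still what a descriptive publication and a meta-analysis use.

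**Conclusion.** The point holds as a gap in the caveat and in the reported uncertainty. The planned analyses omit between-period variation. For any non-zero period variance their nominal intervals are too narrow and the long-run type I error exceeds 5%. Bias in this one trial may run either way. The section's sole caution about the control does not convey this, and the parallel-group and straightforward wording contradicts it.

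The size cannot be derived from the documents. Under the assumed 15-20% composite rate, coverage is about 93% at τ = 3 points and 87-89% at 5.7 points.

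Two stronger inferences are not supported: that the plan asserts a conservative comparison, and that its P values will necessarily be too small. This is an inexpensive improvement to a pilot, not a flaw that invalidates it.

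**What to change.** 1. **Wording.** Replace the sentence on impaired significance, and the parallel-group and straightforward wording, with a statement that the comparison is non-concurrent. It should say that P values and intervals are nominal and omit between-period variation, so uncertainty is understated, and that bias may run in either direction.

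2. **One sensitivity table per co-primary endpoint**, fixed before analysis:
   - Shift the control result by pre-set amounts in both directions (for example ±3, ±6 and ±10 points for the composite; ±2, ±3 and ±5 mL/min/1.73 m² for GFR). Report the shift at which the conclusion changes.
   - Give intervals based on √(SE² + τ²) over a stated range of assumed τ. This part is needed because shifting a control mean by a constant moves the estimate but leaves its standard error, and so its meta-analytic weight, unchanged.

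   Publish the table with the estimate so that meta-analysts have a usable standard error.

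No new patients, visits or data are required. The cost is a little more analysis and reported uncertainty that looks less favourable.

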q. Compare the incidence of the development of donor specific antibody (DSA) in the first 24 months post-transplant in the experimental arm to the historical control arm.

Population:

Patients will include all patients age 18 or over who are receiving renal transplantation regardless of prior transplant, ECD kidney, living donor kidney, level of sensitization, or BMI.

Inclusion Criteria: At Screening: (2 months to 6 months after transplantation \pm 10 days)

- Male or female renal allograft recipients at least 18 years old.
- Patients who have given written informed consent to participate in the study. If consent cannot be expressed in writing, it must be formally documented and witnessed, ideally via an independent trusted witness.
- Patient who has received a kidney transplant from a deceased or living unrelated-/related donor.
- Recipient of a kidney allograft with a cold ischemia time (CIT) < 36 hours.
- Female patients must have a negative pregnancy test prior to study enrollment.
- Patients on CNI (tacrolimus and myfortic®) without steroid maintenance following Campath® induction.
- Patients with an acceptable allograft function defined by a serum creatinine < 2.5 mg/dL (250 μ mol/L) and an actual eGFR (MDRD4) \geq 30 mL/min/1.73m² (without renal replacement therapy).
- No evidence of rejection since the time of transplantation.

Exclusion criteria At Screening: (2 months to 6 months after transplantation \pm 10 days)

- Recipient of ABO incompatible allograft or a positive cross-match.
- Patient who is human immunodeficiency virus (HIV) positive.
- Patient who received an allograft from a Hepatitis B surface Antigen (HBsAg) or a Hepatitis C Virus (HCV) positive donor.

- HBsAg and/or a HCV positive patient with evidence of elevated LFTs (ALT/AST levels ≥ 2.5 times ULN). Viral serology results obtained within 6 months prior to screening are acceptable.
- Patient with severe restrictive (TLC $< 50\%$) or obstructive pulmonary (FEV1 < 50) disorders.
- Patient with severe allergy requiring acute (within 4 weeks of baseline) or chronic treatment that would prevent patient from potential exposure to everolimus, or with hypersensitivity to drugs similar to everolimus (e.g. macrolides).
- Patients with a known hypersensitivity/contraindication to any of the immunosuppressants or their classes, or to any of the excipients.

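### The Statistical Section calls a single arm with unmatched, non-concurrent historical controls a parallel-group study and leaves adjustment of the 24-month eGFR co-primary optional

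*Combined protocol and SAP*

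**What the plan says.** **Design.** Study Design items 1, 2 and 4 set out a single-centre pilot with one treatment arm, 55 patients enrolled over five years, and a historical control. Item 10 draws about 50–55 controls from patients transplanted at the centre between October 2011 and the start of the trial. It uses every eligible patient, rules out matching, and keeps patients who decline the trial out of the control group. The Statistical Section nevertheless states: "This trial is designed as a parallel-group study. Analysis of data for this design is simple and interpretation of the result is straightforward".

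**Caveats.** Study Purpose and Rationale says "This is a small pilot study; multiple comparisons will be made for descriptive purposes only". The Statistical Section says that the study is not powered for significance and adds "The statistical significance will also be impaired by the use of a historical control group".

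**Endpoint and analysis.** Co-primary (b) is "Renal function at 24 months post transplantation using GFR as measured by the Modified Diet Renal Disease (MDRD) estimation". For continuous outcomes the Statistical Section says that, with so few patients, "it may not be meaningful to apply analysis of (co)variance for the statistical evaluation" of variables "such as creatinine clearance, but we will attempt to use this method with the guidance of our statistician". It names no covariate, and its example variable is creatinine clearance rather than MDRD eGFR.

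**Entry.** Inclusion and exclusion are judged "At Screening: (2 months to 6 months after transplantation", with a 10-day tolerance. The renal criterion is "Patients with an acceptable allograft function defined by a serum creatinine < 2.5 mg/dL" together with an eGFR of at least 30, and there must have been no rejection since transplantation.

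**The concern.** A parallel-group comparison is easy to interpret because the groups are concurrent and, usually, randomised. Here they are neither. Trial patients select themselves by consent at 2–6 months, and controls come from an earlier period. Differences in case mix, calendar time and willingness to take part can all move the eGFR difference.

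The plan's caveats do not cover this. Low power and impaired significance describe an imprecise estimate; bias describes one that is off target. The Statistical Section intends publication whatever the result, so that the data can enter meta-analysis. Pooling reduces imprecision but carries bias forward.

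Without randomisation or matching, pre-set adjustment is the main analytic protection against measured case-mix differences. If it remains optional, with covariates unnamed, the co-primary result can depend on choices made after the data are seen.

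**Working it through.** **1. The plan's own figure.** 11 patients per year × 5 years = 55, and 5 + 2 years of follow-up = 7 years. Both agree with Study Duration. This is accrual arithmetic; the documents give no effect size, eGFR standard deviation or power to reproduce.

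**2. Do the eligibility criteria equalise entry function?** They bound it (creatinine below 2.5 mg/dL, eGFR at least 30) and do not fix its mean. Prior transplants, extended-criteria kidneys and any level of sensitisation are admitted, so two groups that both pass can differ in average entry eGFR.

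**3. Size of the bias (assumed inputs, none in the documents).** Let D = 5 mL/min be the group difference at entry and r = 0.5–0.7 the within-group correlation between entry and 24-month eGFR, with equal SDs at both times.

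| Model | Unadjusted bias | Left after adjusting for entry eGFR |
|---|---|---|
| A: imbalance acts only through measured entry eGFR | r × D = 0.5 × 5 = 2.5 to 0.7 × 5 = 3.5 | 0, by construction |
| B: stable difference D, entry eGFR measures it with reliability r | D = 5 | (1 − r) × D = 0.5 × 5 = 2.5 to 0.3 × 5 = 1.5 |

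No formula contains the sample size, so this is not a matter of power. Unmeasured confounding is untouched in both models.

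**4. Are there enough patients to adjust?** An eGFR analysis restricted to working grafts loses patients. Background and Preliminary Data gives two-year death-censored graft survival of 85.6% and patient survival of 90.6% on tacrolimus plus myfortic. Taking the product as a rough retention rate: 105 × 0.856 × 0.906 ≈ 81, where 105 = 55 + 50. A model with intercept, group, entry eGFR, donor type, age and race (the two categorical factors each in two levels) has six parameters, leaving 81 − 6 = 75 residual degrees of freedom. Those rates come from a 2006–2007 cohort and include early losses, which trial entry at 2–6 months excludes. Small numbers do not prevent a short covariate list.

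**5. Control index time.** Item 10 carries the 2–6 month screening window over to controls through the shared criteria, but does not say when within it a control is assessed. A trial patient entering at month 6 has been rejection-free for six months; a control assessed at month 2 need only have been so for two.

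**6. Which 24 months?** Objectives and Study Design item 6 count from transplantation. In the visit table, month 1 follows a baseline visit that itself follows screening at 2–6 months, so the months appear to run from baseline. If so:
- the month-24 visit falls at 24 + 2 = 26 to 24 + 6 = 30 months post transplantation;
- 24 months post transplantation falls at treatment months 24 − 6 = 18 to 24 − 2 = 22;
- the nearest scheduled visit is month 18 or 21, at most 1.5 months away before visit windows (entry at 4.5 months gives 19.5).

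A usable creatinine is therefore scheduled, but no rule selects it.

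**The case against.** The other side has real material.

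- **Mitigation exists.** Item 10 starts the control period in October 2011 precisely because the five-day steroid taper was introduced then, so one known era difference is handled by design. Centre, eligibility criteria and pre-conversion regimen are also shared, and the expectation of similar demographics is argued from the shared criteria. A reader might infer that the plan ignores comparability; it does not. What remains is variation within the eligibility limits, later drift in practice, and consent.
- **The label hides little.** The Statistical Section itself mentions the historical control shortly before calling the design parallel-group, and again afterwards. Alone, the label is a wording correction. The claim of straightforward interpretation is harder to excuse.
- **Multivariable modelling was in view.** The covariance sentence cites a tutorial on multiple linear regression (reference 19), and Cox regression is planned for graft survival. A reader might infer that no adjustment was intended; the documents do not support that. The gap is that adjustment is hedged and no covariates are fixed.
- **The study is a descriptive pilot.** This lowers the stakes, but a descriptive difference still misleads if it reflects case mix.
- **Graft loss and death are not overlooked.** Both are components of co-primary (a), so a reader should not conclude that they go unreported. The eGFR result needs only to be labelled and read beside that endpoint.
- **The timing gap is small.** It is 1.5 months at most, with no demonstrated effect on eGFR. The contradiction between clocks still needs resolving, because using the month-24 visit unexamined could move the assessment to 26–30 months in the trial arm only.

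**Conclusion.** The point holds. The Statistical Section misdescribes the design, its caveats omit bias, and the eGFR co-primary has no committed adjusted analysis. Small numbers are not a sufficient reason for that: about 75 residual degrees of freedom would remain on a rough retention estimate from an earlier cohort.

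The 2.5–5 mL/min unadjusted bias is an illustration. It rests on an assumed 5 mL/min imbalance and r = 0.5–0.7, and scales directly with the imbalance. Nothing in the documents shows that the groups do differ at entry, so a reader should not infer that the trial's result is biased, or in which direction. Nor should ANCOVA be read as a cure: under measurement error 1.5–2.5 mL/min of the assumed 5 remains, and calendar-time or consent effects not captured by the covariates remain in full. The reading of the visit table as running from baseline is an inference from its layout.

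The change is worth making, but the problem is not fatal to a descriptive pilot.

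**What to change.** 1. **Wording.** Replace the two sentences with a statement that this is a single-arm study with a non-randomised comparison to a non-concurrent historical control, subject to confounding, calendar-time and consent-selection bias that adjustment can reduce but not remove.
2. **Analysis.** Make the main analysis of co-primary (b) an ANCOVA of 24-month MDRD eGFR on group, adjusted for entry eGFR and a short list fixed in advance (for example donor type, recipient age and race). Label it as describing patients with a working graft, to be read beside co-primary (a).
3. **Control index times.** Assign them to follow the trial arm's distribution of entry times over 2–6 months, and apply every eligibility rule, including no prior rejection, at that time. The distribution is complete only when enrolment closes, so the assignment method should be fixed beforehand.
4. **Clock.** Reconcile Objectives and Study Design item 6 with the visit table, and use one window around 24 months post transplantation for choosing the eGFR value in both groups.

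**Cost.** Text changes, plus chart abstraction for about 50–55 controls (24-month creatinine, donor type, age, race). Entry creatinine is already needed to apply the renal criterion to controls, and trial-arm creatinine is scheduled at every visit. Some controls may be lost if they are ineligible at their index time. Bias from measurement error and unmeasured confounding will remain.
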